5.5.2 Dispensing the investigational treatment

Each study site will be supplied by Novartis with investigational treatment labelled according to legislation in France related to clinical trial product.

5.5.3 Handling of study treatment

5.5.3.1 Handling of investigational treatment

Investigational treatment must be received by a designated person at the study site, handled and stored safely and properly, and kept in a secured location to which only the investigator and designees have access. Upon receipt, all investigational treatment should be stored according to the instructions specified on the labels. Clinical supplies are to be dispensed only in accordance with the protocol.

Medication labels will be in the local language and comply with the legal requirements. They will include storage conditions for the investigational treatment but no information about the patient.

The investigator must maintain an accurate record of the shipment and dispensing of investigational treatment in a drug accountability log. Monitoring of drug accountability will be performed by the field monitor during site visits and at the completion of the trial.

At the conclusion of the study, and as appropriate during the course of the study, the investigator will return all unused investigational treatment, packaging, drug labels, and a copy of the completed drug accountability log to the Novartis monitor or to the Novartis address provided in the investigator folder at each site.

5.5.3.2 Handling of other study treatment

Not applicable.

5.5.4 Instructions for prescribing and taking study treatment

All dosages prescribed and dispensed to the patient and all dose changes during the study must be recorded on the Dosage Administration Record CRF.

5.5.5 Permitted dose adjustments and interruptions of study treatment

Study drug dose adjustments and/or interruptions are permitted, according to the investigator judgment. These changes must be recorded on the Dosage Administration Record CRF.

5.5.6 Rescue medication

Not applicable

5.5.7 Concomitant treatment

The investigator should instruct the patient to notify the study site about any new medications he/she takes after the start of the study drug.

5.5.8 Prohibited Treatment

The expression of hepatic CYP450 enzymes may be suppressed by the cytokines that stimulate chronic inflammation, such as IL-1 beta. Thus, CYP450 expression may be reversed when potent cytokine inhibitory therapy, such as canakinumab, is introduced. This is clinically relevant for CYP450 substrates with a narrow therapeutic index where the dose is individually adjusted. In patients being treated with this type of medicinal product while on canakinumab, therapeutic monitoring of the effect or of the active substance concentration should be performed and the individual dose of the medicinal product adjusted as necessary.

Use of canakinumab with TNF inhibitors is not recommended because this may increase the risk of serious infections (an increased incidence of serious infections has been associated with administration of another IL-1 blocker in combination with TNF inhibitors)

No data are available on either the effects of live vaccination or the secondary transmission of infection by live vaccines in patients receiving canakinumab. Therefore, live vaccines should not be given concurrently with canakinumab, but prior to initiating Ilaris[®] therapy.

5.5.9 Discontinuation of study treatment and premature patient withdrawal

Patients may voluntarily withdraw from the study for any reason at any time. Study treatment must be discontinued under the following circumstances:

- The availability of repaid product in France for the patient's disease,
- If, on balance the investigator believes that continuation would be detrimental to the patient's well-being,
- Unsatisfactory therapeutic effect based on investigator judgment,
- Use of prohibited treatment / Protocol violation,
- Onset of malignancy,
- Occurrence of an uncontrolled life-threatening infection,
- Pregnancy,
- Other Adverse Event needing study discontinuation,
- Lost to follow-up,
- Administrative reasons,

- Death.

If premature withdrawal occurs for any reason, the investigator must make every effort to complete End of study visit in the CRF and to determine the primary reason for a patient's premature withdrawal from the study and record this information.

5.5.10 Emergency breaking of treatment assignment

Not applicable

5.5.11 Early study termination

The study can be terminated at any time for any reason by Novartis. Should this be necessary, the patient should be seen as soon as possible and treated for a prematurely withdrawn patient. The investigator may be informed of additional procedures to be followed in order to ensure that adequate consideration is given to the protection of the patient's interests.

6 Visit schedule and assessments

Visits will take place at the patient's scheduled drug administration date (approximately every 4 weeks or less frequently according to investigators judgment i.e. 6, 8 or 12 weeks).

If no administration is performed within the 12 weeks of previous injection, a control visit will be performed at Week 13 +/- 7 days after the last administration in order to evaluate safety and need for the patient to continue the treatment and the study.

Table : scheduled visits and evaluations

Visits	Inclusion ⁽¹⁾	Visits for canakinumab administration ⁽⁴⁾	End of the study visit ⁽²⁾
Visit window (days)	+/- 7	+/- 7	+/- 7
Inclusion/ exclusion criteria	X		
Written informed consent	X		
Demographic data	X		
Treatment administration	X	X	X
Concomitant treatment	X ⁽³⁾	X	X
Adverse events		X	X
End of the study			X

- 1) The date of last visit of CACZ885G2301E1/CACZ885N2301/CACZ885G2306 study will be the first visit of this extension study.
- 2) The end of study is defined as premature termination or end of the study according to protocol: in the month following the availability of repaid product in France.
- 3) Corticosteroids and methotrexate only.
- 4) Visits will take place at scheduled administration date every 4, 6, 8 or 12 weeks (section 5). Dose interval may be prolonged during the study (i.e. visits every 6, 8 or 12 weeks or longer in case of adequate response at the discretion of the investigator (section 5). If no administration is performed within the 12 weeks of previous injection, a control visit will be performed at Week 13 +/- 7 days after the last administration in order to evaluate safety and need for the patient to continue the treatment and the study.

6.1 Patient demographics/other baseline characteristics

Demography information and other baseline characteristics are those collected in CACZ885G2301E1 / CACZ885N2301 / CACZ885G2306 study.

6.2 Study treatment dispensation

Basic study treatment dispensation data will be collected (date of injection and total volume injected).

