In case of use of oral contraception women should have been stable on the same pill for a minimum of 3 months before taking study treatment.

Reliable contraception should be maintained throughout the study and until 3 months after canakinumab discontinuation.

5 Treatment

Initial canakinumab dose:

For patients previously included in study CACZ885G2301E1 (SJIA)

Patients will continue the same dose as their last dose administered in the study CACZ885G2301E1: canakinumab 4mg/kg (or 300mg max) or 2mg/kg (150mg max) every 4 weeks.

Canakinumab dose reduction from 4 mg/kg to 2 mg/kg every 4 weeks in steroid-free patients with prolonged strong response was permitted in the ongoing extension study CACZ885G2301E1 at the request of the treating physician and with the agreement of Novartis.

Similarly, in this study, the canakinumab dose may be reduced from 4mg/kg (300 mg max) to 2mg/kg (150 mg max) every 4 weeks and then interrupted after a prolonged remission according to the investigators judgment.

For patients previously included in study CACZ885N2301 (Periodic Fever syndromes indications: TRAPS, HIDS or crFMF)

Patients will continue one of the following regimens as received at the end of the study:

- canakinumab 150 mg (or 2 mg/kg for patients weighing ≤ 40 kg) q4w
- canakinumab 150 mg (or 2 mg/kg for patients weighing ≤ 40 kg) q8w
- canakinumab 300 mg (or 4 mg/kg for patients weighing ≤ 40 kg) q4w
- canakinumab 300 mg (or 4 mg/kg for patients weighing ≤ 40 kg) q8w

In case of re-flare (according to investigators judgment), patients will be allowed to increase the dose as follow:

- If patients receive canakinumab 150 mg q8w, the dose of canakinumab will be increased to 150 mg q4w
- If patients receive canakinumab 150 mg q4w, the dose of canakinumab will be increased to 300 mg q4w
- If patients receive canakinumab 300 mg q8w, the dose of canakinumab will be increased to 300 mg q4w

For patients previously included in study CACZ885G2306 (SJIA):

The patients will continue the same dose as their last dose administered at the end of the tapering period study CACZ885G2306.

Then, patients will continue one of the following regimens:

- Canakinumab 4mg/kg q4wks
- Canakinumab 2mg/kg q4wks
- Canakinumab 1mg/kg q4wks
- Canakinumab 4mg/kg q8wks
- Canakinumab 4mg/kg q12wks

The patients who have withdrawn canakinumab per protocol may resume canakinumab after a relapse at a starting dose of 4 mg/kg (maximum 300 mg) every 4 weeks.

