2.1.1 General definitions

Study treatment: refers to: Ilaris = ACZ885

Study treatment start and end date: Study treatment start date is defined as the first date of study drug is administered and recorded on the Study Medication Dosing Record in CRF page. Similarly, study drug end date is defined as the last date of study drug is administered.

Study day: Study day will be calculated as (event date – study drug start date + 1 day) for events that occurred on or after study drug start date (e.g. visit, adverse events). For events prior to study drug start date (e.g., time of diagnosis), study day will be negative and calculated as (event date – study drug start date).

Baseline and post baseline: In general, a *baseline* value refers to the last measurement made prior to administration of the first dose of study treatment or the average values taken prior to administration of the first dose of study treatment. A post-baseline value refers to a measurement taken after the first dose of study treatment.

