2.4 Treatments (study treatment, rescue medication, concomitant therapies, compliance)

2.4.1 Study treatment / compliance

The maximal total single dose of canakinumab (ACZ885) allowed is 300 mg, which is administered as two subcutaneous 150 mg injections once every 4 weeks.

The canakinumab dose interval (i.e. every 6, 8 or 12 weeks) may also be prolonged in patients with adequate response according to the clinical response and investigators judgment.

The extent of exposure will be examined to determine the degree to which safety can be assessed for canakinumab (ACZ885). The extent of exposure to study drug will be characterized according to the duration of exposure and the number of patients exposed.

Duration of exposure to the treatment will be calculated as the number of days between the first dose date and the last dose date exposed to that treatment over the specified period in Ilaris (ACZ885GRR01) study, expressed as: Duration of exposure = ((Date of last known dose of study drug – Date of first dose of study drug) – Number of days interrupted) + 1.

The duration of exposure (in days) and the cumulative volume administered (in mL) will be summarized with descriptive statistics (n, mean, median, standard deviation, minimum, maximum, Q1, Q3) for the safety set.

The total number of doses (injections) administered, number of 2 mg/kg doses administered, number of 4 mg/kg doses administered will be summarized with number and percentage for overall, 2mg/kg and 4 mg/kg dose group for safety set. By subject listing along with dose date will be provided for safety set.

The duration of exposure (in days) and number of injection will be summarized for the safety set as

- a continuous variable with the standard descriptive statistics
- a categorical variable for number of does (injections) administered classified into 1-4, 5-8, 9-12, 13-16, 17-20, 21-24 with number and percentage for below group.
 - Number of doses (injections) administered
 - Number of 1 mg/kg q4w doses administered
 - Number of 2 mg/kg q4w doses administered
 - Number of 4 mg/kg q4w doses administered
 - Number of 2 mg/kg q8w doses administered
 - Number of 4 mg/kg q12w doses administered
 - Other dose administered
 - No dose administered
- Number of subject and percentage at baseline, reduction in dose at end of study, increase in dose at end of study and stable dose with all dose amount.

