5.5 Rule of exclusion criteria of analysis sets

All protocol deviations defined at the start of the study are listed with associated population codes in below table. The list will be updated before CDBL.

Protocol Deviation ID	Protocol Deviation Description	Population code
I01	Written informed consent was not obtained before performing any assessment.	1
M01	Patient took prohibited concomitant medication	0
E01	Pregnant or nursing female patients, where pregnancy is defined as state of a female after conception and until termination of gestation, confirmed by +ve hCG laboratory test or urinary pregnancy test	0
S01	Canakinumab not administered as per protocol dosage different than 2mg/kg or 4 mg/kg	0
S02	Canakinumab not administered per protocol schedule. Difference between the dose on consecutive visits (dd-mmm-yyyy) and (dd-mmm-yyyy) is not between 6 weeks to 8 weeks.	0
	No treatment is taken.	1

6 Reference

Clinical Study Protocol CACZ885G2301E1: An open-label extension study of canakinumab (ACZ885) in patients with Systemic Juvenile Idiopathic Arthritis (SJIA) and active systemic manifestations who participated in studies ACZ885G2301 and ACZ885G2305; and response characterization study in canakinumab treatment-naïve patients with active SJIA with and without fever

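### SAP dose categories and deviation rule S01 do not match the regimens the protocol permits, and delivered mg/kg cannot be checked from the data the protocol names

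*Protocol*

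**What the plan says.** **Regimens.** Protocol section 5 (Treatment) lists starting regimens by parent study.
- CACZ885G2301E1: 4 or 2 mg/kg every 4 weeks, with maximum doses in mg.
- CACZ885N2301 (periodic fever): four regimens, for example "canakinumab 150 mg (or 2 mg/kg for patients weighing ≤ 40 kg) q4w". The others are 150 mg every 8 weeks and 300 mg every 4 or 8 weeks, with 2 or 4 mg/kg replacing the flat dose at 40 kg or less.
- CACZ885G2306: 4, 2 or 1 mg/kg every 4 weeks, and 4 mg/kg every 8 or 12 weeks.

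**Analysis.** SAP 2.4.1 summarises the "number of 2 mg/kg doses administered, number of 4 mg/kg doses administered". It then tabulates 1, 2 and 4 mg/kg every 4 weeks, 2 mg/kg every 8 weeks, 4 mg/kg every 12 weeks, Other and none. It also summarises "the cumulative volume administered (in mL"). Deviation S01 in SAP 5.5 reads "Canakinumab not administered as per protocol dosage different than 2mg/kg or 4 mg/kg" and carries population code 0.

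**Data.** Protocol 6.2: "Basic study treatment dispensation data will be collected (date of injection and total volume injected"). The visit table in Protocol section 6 has no body-weight row. Protocol 9.2 names sex and date of birth as the items collected again. Protocol 5.5.4 adds: "All dosages prescribed and dispensed to the patient and all dose changes during the study must be recorded on the Dosage Administration Record CRF". Protocol 5.5.5 says of adjustments and interruptions: "These changes must be recorded on the Dosage Administration Record CRF".

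**The concern.** The SAP sorts doses with a list that is not the protocol's list. A programmer who follows S01 as worded would flag patients who received exactly what the protocol allows. SAP 2.3.2 tabulates the number and percentage of patients with deviations, and Protocol section 11 sends significant deviations to the study report, so the error would reach reported counts. Protocol 9.3 also promises exposure by dose. A table that sends regularly prescribed regimens to Other does not deliver that.

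A second, smaller weakness concerns verification. S01 is about the dose administered, in mg/kg. Date and volume give mg for a known concentration, but not mg/kg without a current weight. Many of these patients are children who grow during an open-ended study.

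**Working it through.** The plan states no figure on this point, so there is none to reproduce. The check has three parts.

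**1. Protocol regimens against the SAP list**

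Inputs: the regimens in Protocol section 5, the categories in SAP 2.4.1, and S01 in SAP 5.5. Flat doses are taken as written.

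| Regimen in Protocol section 5 | Own category in SAP 2.4.1? | Flagged by S01 as worded? |
|---|---|---|
| 4 mg/kg q4w | yes | no |
| 2 mg/kg q4w | yes | no |
| 1 mg/kg q4w | yes | **yes** |
| 2 mg/kg q8w | yes | no |
| 4 mg/kg q8w | **no** | no |
| 4 mg/kg q12w | yes | no |
| 150 mg flat q4w | **no** | **yes** |
| 150 mg flat q8w | **no** | **yes** |
| 300 mg flat q4w | **no** | **yes** |
| 300 mg flat q8w | **no** | **yes** |

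Five of ten listed regimens have no category, and five of ten are flagged. The 1 mg/kg row is a contradiction inside the SAP: 2.4.1 counts it as a regimen and 5.5 treats it as a deviation.

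Now suppose that 150 mg is read as 2 mg/kg and 300 mg as 4 mg/kg, a mapping the SAP does not state. S01 then flags one of ten (1 mg/kg q4w). Two of ten still lack a category (4 mg/kg q8w and 300 mg q8w).

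**2. Flat doses expressed in mg/kg**

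Formula: mg/kg = mg / weight. The weights are assumed for illustration, because the documents give none.

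| Weight (assumed) | 150 mg | 300 mg |
|---|---|---|
| 41 kg | 150/41 = 3.7 | 300/41 = 7.3 |
| 60 kg | 150/60 = 2.5 | 300/60 = 5.0 |
| 75 kg | 150/75 = 2.0 | 300/75 = 4.0 |

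Only at 75 kg do the flat doses equal the 2 and 4 mg/kg that S01 accepts.

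Ceiling on flat-dose patients: Protocol section 4 allows up to 8 periodic-fever patients of 41, and 8/41 = 19.5%. The synopsis allows up to 7 of 40, and 7/40 = 17.5%. Flat dosing applies only above 40 kg, and Protocol 1.1 says the parent study enrolled from age 2, so the true number may be lower. Up to 21 patients may come from CACZ885G2306; how many are on 1 mg/kg q4w or 4 mg/kg q8w is not stated.

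**3. What volume and date can show**

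Formula: mg = mL × 150. The strength is the one Protocol 5.1.1 gives for the solution; using it for the reconstituted lyophilisate would be an assumption.
- 1.0 mL = 150 mg, which is 4 mg/kg at 37.5 kg, 3 mg/kg at 50 kg and 2 mg/kg at 75 kg.
- 0.5 mL = 75 mg, which is 4 mg/kg at 18.75 kg, 2 mg/kg at 37.5 kg and 1 mg/kg at 75 kg.

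One volume therefore fits several dose groups. A weight carried forward from the parent study does not solve this. After assumed growth of 25% or 50%, a true 2 mg/kg dose appears as 2 × 1.25 = 2.5 or 2 × 1.5 = 3.0 mg/kg.

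The unit also matters for the planned split into reduced, increased and stable dose. A child kept on 4 mg/kg who grows from 20 to 30 kg (assumed) goes from 80 to 120 mg. That is stable in mg/kg and an increase in mg or mL.

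**The case against.** A reader might infer that only date and volume are collected, so that the dose-group tables cannot be produced at all. The documents do not support that. Protocol 6.2 calls these basic data and does not say they are the only data. Protocol 5.5.4 and 5.5.5 put prescribed and dispensed dosages and dose changes on a CRF, and SAP 2.1.1 refers to dates "recorded on the Study Medication Dosing Record in CRF page". The SAP categories combine dose and interval, so they read as regimen labels and need no calculation from volume. The CRF is not among the documents, so a unit or weight field on it cannot be ruled out. This objection stands, and it limits the data point to verification.

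A reader might also infer that the adverse event results are compromised. They are not. Adverse events are summarised by disease, no adverse event table by dose group is planned, and the SAP gives other context such as duration of exposure and concomitant medication. Nor is any patient left without a category, because Other exists.

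It can further be said that S01 is harmless. Population code 0 keeps everyone in the Safety Set, and SAP 5.5 says the deviation list will be updated before database lock. The presence of 2 mg/kg q8w among the SAP categories also suggests that its author had a flat-dose pairing in mind, since Protocol section 5 lists that regimen only for periodic fever. These points reduce the consequence. They do not remove the mismatch: the pairing is not written down, 1 mg/kg q4w is flagged even under it, and 4 mg/kg q8w has no category under either reading.

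**Conclusion.** The concern holds as a mismatch between SAP and protocol. Followed as written, the SAP would report permitted doses as deviations and put listed regimens into Other. By regimen, the size is five of ten on each count if flat doses are taken as written. If the unstated pairing is assumed, it is one of ten flagged and two of ten without a category. By patient, the size is unknown: 8 of 41 is a ceiling for flat doses, and the numbers on 1 mg/kg q4w and 4 mg/kg q8w are not given.

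The data point is secondary. Dose groups can be tabulated from the recorded regimen if its unit allows. Delivered mg/kg cannot be checked from the data that the protocol names. This rests on the protocol text alone, since the CRF was not available.

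The effect is on deviation counts and the exposure tables. The Safety Set and the adverse event counts do not change.

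**What to change.** 1. In SAP 2.4.1, define the dose groups by the regimens in Protocol section 5. Pair flat 150 mg with 2 mg/kg and flat 300 mg with 4 mg/kg at each interval as reporting groups, and add 4 mg/kg q8w. State that groups come from the prescribed regimen recorded under Protocol 5.5.4.
2. Reword S01 so that it compares the administered dose with the patient's own prescribed protocol regimen.
3. Summarise cumulative dose in mg alongside mL, and state the concentration used for each pharmaceutical form.
4. State the unit and interval of the dosage on the dosing CRF. Where source notes already hold the weight used for prescribing, record it with the dose.

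Cost: items 1 to 3 are SAP text, and item 2 fits the update already planned before database lock. Item 4 is a small CRF change. It needs an amendment under Protocol 11.1, new paper pages, and some retrieval of past weights. It adds no patient procedure. If item 4 is judged too costly, items 1 and 2 alone still correct the reported counts, and the report should then say that delivered mg/kg was not verified.

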6.3 Efficacy

No efficacy data are collected in this study.

6.4 Safety

Safety assessments will consist of recording and monitoring of Adverse Events (AE) and Serious Adverse Events (SAE).

7 Safety monitoring

7.1 Adverse events

An adverse event (AE) is any untoward medical occurrence (i.e., any unfavorable and unintended sign [including abnormal laboratory findings], symptom or disease) in a subject or clinical investigation subject *after providing written informed consent* for participation in the study. Therefore, an AE may or may not be temporally or causally associated with the use of a medicinal (investigational) product.

The occurrence of adverse events should be sought by non-directive questioning of the patient at each visit during the study. Adverse events also may be detected when they are volunteered by the patient during or between visits or through physical examination, laboratory test, or other assessments.

Abnormal laboratory values or test results constitute adverse events only if they fulfill at least one of the following criteria:

- they induce clinical signs or symptoms,
- they are considered clinically significant,
- they require therapy.

Adverse events should be recorded in the Adverse Events CRF under the signs, symptoms or diagnosis associated with them, accompanied by the following information:

- the severity grade
 - mild: usually transient in nature and generally not interfering with normal activities
 - moderate: sufficiently discomforting to interfere with normal activities
 - severe: prevents normal activities
- its relationship to the study medication
- study treatment (no/yes), or
- investigational treatment (no/yes), or
- the other study treatment (non-investigational) (no/yes), or
- both or indistinguishable,
- its duration (start and end dates) or if the event is ongoing an outcome of not recovered/not resolved should be reported

- whether it constitutes a serious adverse event (SAE - See section 7.2 for definition) action taken regarding canakinumab treatment.

All adverse events should be treated appropriately. Treatment may include one or more of the following:

- no action taken (i.e. further observation only)
- study treatment dosage adjusted/temporarily interrupted
- study treatment permanently discontinued due to this adverse event
- concomitant medication given
- non-drug therapy given
- patient hospitalized/patient's hospitalization prolonged
- its outcome (not recovered/not resolved; recovered/resolved; recovering/resolving, recovered/resolved with sequelae; fatal; or unknown)

Once an adverse event is detected, it should be followed until its resolution or until it is judged to be permanent, and assessment should be made at each visit (or more frequently, if necessary) of any changes in severity, the suspected relationship to the study treatment, the interventions required to treat it, and the outcome.

Information about common side effects already known about the investigational drug can be found in the SmPC or will be communicated between SmPC updates in the form of Investigator Notifications. This information will be included in the patient informed consent and should be discussed with the patient during the study as needed.

The investigator should also instruct each patient to report any new adverse event (beyond the protocol observation period) that the patient, or the patient's personal physician, believes might reasonably be related to study treatment. This information should be recorded in the investigator's source documents. However, if the AE meets the criteria of an SAE, it must be reported to Novartis.

